 - a. *Community-based OUD treatment centers (Centers).* A total of 30 centers will be included as part of the proposed study (see Attachments: Letters of Support). Centers were selected because they met the following inclusion criteria: a) prescribe FDA-approved medication to treat adult patients with OUDs; b) enroll 5+ new patients per month; and c) have at least 2 staff who provide psychosocial support to OUD patients.
 - b. *Community-based OUD treatment center providers (CM Providers).* Drs. [name] and [name] will work with each participating opioid treatment center to identify front-line treatment providers and leaders eligible for the study.

Eligible providers will be any front-line treatment provider who has: a) been involved in providing psychosocial support to OUD patients on pharmacotherapy, b) an active caseload, c) been employed by the opioid treatment center at least 3 months, and d) willingness to commit to 14 months of CM training and support. All eligible treatment providers at the centers will be invited to receive the CM didactic training. However, centers will nominate 2-5 providers to serve as “CM champions”: the “CM champions” will complete periodic measures of organizational climate (described further in Measures), submit monthly audio recordings of their sessions, receive performance feedback on their audio recordings, and (for those randomized to E-ATTC) will receive performance incentives. In our experience with centers in a recent pilot study, none had more than 5 staff, so for the vast majority of sites, we expect to be able to invite all staff to participate. Thus, between 60-150 CM Providers (30 centers x 2-5 CM Providers per center) will complete measures across the three cohorts (20-50 CM Staff per cohort).

Eligible leaders will be: a) responsible for supervising frontline CM Staff, b) have been employed by the opioid treatment center at least 6 months, and c) be willing to commit to 14 months of external leadership coaching. Thus, in addition to the 60-150 CM providers, another 60 leadership staff (30 centers x 2 leaders per center) will provide data.

There is an annual staff turnover rate of approximately 30% among substance use disorder treatment providers and 20% among leadership staff. Although we invite 2-5 front-line providers from each center to participate in the study, we allow each center to send as many providers to the CM training as desired. Given the likelihood that about

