 - b. *Implementation.* During this 9-month phase, trained CM providers in both conditions begin implementing the CM protocol with patients. Additionally, in both conditions, CM providers will submit an audio recording of at least 1 CM session per month and will receive ongoing performance feedback on their CM competence from an ATTC trainer. More specifically, each month one CM session recording per CM will be submitted for review using Virtru encrypted email. Once received, a research staff member will rate the session using the 9-item **CM Competence Scale** (CMCS) for Reinforcing Compliance.¹² Once the rating has been done, CM providers will be emailed feedback reports. Staff will also participate in condition-specific monthly group coaching calls. Centers randomized to E-ATTC will receive two additional elements of support: (1) ELC and (2) P4P incentives. Throughout Implementation, as part of ELC, each center leadership will participate in monthly center-specific coaching calls. As part of P4P, CM providers will receive monetary bonuses for achieving two pre-defined goals based on benchmarks in RCT research with OUD counselors: (a) CM Exposure¹³ (i.e., meeting a target number of 10 sessions per patient) and (b) CM Competence¹⁰ (i.e., meeting a target score of 5.8 on the CMCS). The provider incentive structure is described more in depth in Section 7b. One month before the end of the Implementation phase, the ELC will return for an in-person sustainment-centered planning meeting.

c. **Sustainment.** No ATTC or E-ATTC activities will be provided during this 12-month phase, though sustainment of activities will be actively measured.

7. Implementation Conditions: ATTC vs. E-ATTC.

a. **ATTC.** Participating staff from all centers will receive the ATTC strategy, under [name] oversight.

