P4P. Consistent with the P4P methods [name] found to be effective,¹⁷ E-ATTC condition CM staff will have the opportunity to earn monetary bonuses for the achievement of two performance measures: CM Exposure and CM Competence. The use of monetary bonuses for performance is consistent with a robust literature base in the field of implementation science demonstrating that providing incentives for provider performance is an effective way to increase the uptake of evidence-based treatment.^{See}

¹⁷ It is also consistent with the approach increasingly taken by health insurance companies to link provider reimbursement to quality metrics. The P4P methods used here draw on a robust literature and the benchmarks are specifically set based on prior research. Based on benchmarks attained by OUD counselors after CM training in prior RCT research,¹⁰ CM providers will earn US \$200 for each patient that receives 10 or more CM sessions (i.e., CM Exposure). This is similar to the behavior and incentive combination (i.e., \$200 for threshold level of treatment exposure) that [name] and colleagues found to be effective.¹⁷ Each site will recruit 25 patients and the number of providers will vary from 2-5. For a provider with 10 patients, the maximum amount a provider could receive for CM Exposure is 10 patients * \$200/patient = \$2,000.

Moreover, providers will earn \$50 each month that they demonstrate competent delivery of the rated CM session, defined as a mean score of at least 5.8 on the CMCS (i.e., CM Competence). This is again the same behavior and incentive combination (i.e., \$50 for competent delivery) that was found to be effective in prior research.¹⁷ The maximum incentive a provider could receive for CM Competence is 9 months * \$50/month = \$450.

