Incentive amounts are designed to enable staff to, on average, earn bonuses that during a 12-month period would comprise about 6% of their mean annual base salary of US \$45,000. Prior P4P research^{18,19} has suggested that bonuses between 4 and 7% are large enough to significantly improve staff performance, yet modest enough to be practical for community treatment centers to implement. Provision of incentives will follow the exact same schedule of provision of performance feedback reports described in 7a. Sessions must be submitted by the last day of the month and must be from that calendar month. Within 2-4 weeks following submission of recordings, providers in the E-ATTC condition will receive email notifications from research staff containing their performance feedback reports, as well as confirmation of their achievement of CM Exposure and CM Competence for the prior month. CM staff enrolled in the E-ATTC condition will receive payments via cash, check, or Clincard.

8. Data Collection Procedures.

- a. *Organizational background form.* Prior to randomization, leaders at each center will collaboratively complete an Organizational Background Form via Qualtrics. Data collected will include, but not be limited to: number of patients, proportion of patients on different OUD medications, number of staff, average staff tenure, and years in operation.
- b. *Staff surveys.* After randomization, CM staff and leadership staff will complete two online Qualtrics surveys: one at the start of the Preparation phase and one at the midpoint of the Implementation phase. The first survey (30-45 minutes) will contain the following measures: Provider Demographics, Organizational Readiness for Change, Attitudes towards CM, and putative mediators (i.e., Implementation Climate, Leadership Engagement). The second survey (15-30 minutes) will only evaluate the putative mediators. Participating staff will receive \$25 for the first and \$20 for the second survey. We attained 82% or higher completion rates on comparable staff follow-up surveys in the New England ATTC pilot.

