- i. **Implementation climate.** A 6-item measure of CM staff and leadership shared perceptions regarding the extent to which the innovation being implemented (i.e., CM) is expected, supported, and rewarded within their center.²⁵ Each item is scored on a 5-point Likert scale. This well-validated, brief measure was developed by Jacobs and colleagues, and following published guidelines, we calculate a scale mean for each staff member.
- ii. **Leadership engagement.** A 4-item measure of CM staff and leadership shared perceptions regarding the extent to which leadership is committed to, involved in, engaged in, and accountable for the implementation of the innovation (i.e., CM). Each item is scored on a 5-point Likert scale. Developed and validated as part of [name] current NIDA-funded project, this measure has demonstrated excellent internal reliability ($\alpha = .94$) and has been shown to be a significant predictor of staff-level implementation fidelity ($\beta = .18, p < .05$).²⁶

d. *Covariates.* We measure potential baseline covariates at the patient, staff, and organization level. These measures are only administered at baseline. Specific measures used include:

- i. **Baseline organization form.** A form measuring baseline characteristics including years of operation, number of patients served, and medications prescribed.
- ii. **Implementation Readiness.** A well-validated 12-item pragmatic measure developed by Shea and colleagues²⁷ will assess readiness to implement CM.
- iii. **CM Attitudes.** A brief measure of attitudes towards CM, as well as providers' perception of its effectiveness and acceptability will be administered. This measure was developed by the NIDA Clinical Trials Network and has been used in multiple NIDA funded studies.
- iv. **Provider demographics.** At the provider-level, we measure staff tenure, education level, and attitudes towards CM.

- v. Patient demographics. At the patient-level, we measure biological sex, race/ethnicity, age, and problem severity.
- vi. Patient clinical characteristics. At baseline, we administer a general measure of global health functioning. This scale was developed by the NIH funded patient-reported outcomes study and is used in multiple NIH funded studies.
- e. *Other Measures*. As noted in prior sections, we also collect some additional measures.

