- b. For the **Primary and Secondary Aims**, we test a series of multilevel models in which patients (Level 1) are embed within staff (Level 2) and within centers (Level 3). Consistent with Raudenbush and Bryk's multilevel modeling approach,³² the proportion of variance to-be-explained at each level will be examined as an initial step. Next, following a decomposed-first strategy that advocates for starting with moderation-focused hypotheses to avoid biases associated with conflated effects,³³ we conduct multilevel regressions testing the extent to which our covariates significantly moderate the hypothesized relationship between condition and outcome. We test covariates at three levels: organizational (e.g., years of operation, number of patients, medications prescribed, implementation readiness), staff (e.g., tenure, education, CM attitudes), and patient (e.g., age, race, biological sex, problem severity). If moderation is not found, covariates will be controlled for as predictors. Condition assignment (ATTC vs. E-ATTC) will be the primary independent measure of interest for analyses. In addition to reporting statistical significance, we will report the effect size (ES) using Cohen's d .³⁴
- c. For the **Exploratory Aim**, we again test a series of 3-level models. For each mediator, the average correlation within group (r_{wg}) will be computed to determine whether aggregation of staff level responses to the organizational-level is warranted. Values of r_{wg} range from -1.00 to 1.00, with values $\geq .60$ representing acceptable agreement.³⁵ Centers with r_{wg} values $< .60$ will be excluded from analysis. Exploratory analyses will apply a Baron and Kenny³⁶ style mediation approach,

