which uses centering within context and includes a group mean at level-3 (CWC[M]).³⁷ Procedurally, first the outcome will be regressed on the condition variable (ATTC vs. E-ATTC) in a multi-level regression. Next, the outcome will be predicted by both condition and the group mean centered mediator (e.g., implementation climate) in a multi-level regression. Third, the mediational effect will be calculated by subtracting the estimated coefficient associated with condition in step two from the estimated coefficient associated with condition in step one. This method will allow the between-group mediation effect to be partitioned from the within-group mediation effect, which is important since between-group mediation is the effect of interest. Although significance of the mediation effect will be calculated using the Freedman and Schatzkin³⁸ *t* statistic, we also will report ES, which are not influenced by power.

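### Leadership Engagement appears to pool leaders' ratings of their own engagement with staff ratings, and only E-ATTC leaders are coached, so part of any mediation found may be leader self-report

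*Combined protocol and SAP*

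**What the plan says.** Section 8.b: "After randomization, CM staff and leadership staff will complete two online Qualtrics surveys", one at the start of Preparation and one midway through Implementation. Both carry the two putative mediators.

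Section 9.c.ii describes Leadership Engagement as "A 4-item measure of CM staff and leadership shared perceptions regarding the extent to which leadership is committed to, involved in, engaged in". Accountability of leadership is the remaining element, and items are on a 5-point scale. The same section reports that the measure predicted staff-level fidelity in the developers' own work (β = .18).

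Section 3.b sets the rater numbers: 2-5 CM providers per center, and "another 60 leadership staff (30 centers x 2 leaders per center) will provide data". Eligible leaders are those who supervise the front-line CM staff.

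Leadership coaching belongs to E-ATTC alone (7.b). Section 6.b says that during Implementation, "as part of ELC, each center leadership will participate in monthly center-specific coaching calls", so coaching is under way at the second survey.

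Section 10.c computes within-group agreement "to determine whether aggregation of staff level responses to the organizational-level is warranted" and excludes centers with r_wg below .60. It then obtains the mediated effect by "subtracting the estimated coefficient associated with condition in step two from the estimated coefficient associated with condition in step one". It plans no score, agreement index or sensitivity analysis by rater role.

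**The concern.** The people who are coached are among the raters of what the coaching is meant to change, and they know that they were coached. If coached leaders come to describe themselves as more committed or accountable, the center score rises in E-ATTC whether or not the staff they supervise notice anything.

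Under the difference-in-coefficients rule, a condition-driven shift in the score, multiplied by the score's within-arm relation to the outcome, is reported as mediation. The error runs in the direction of the Exploratory Hypothesis. The trial aims to explain why implementation strategies work, and this score carries half of that explanation. The Primary and Secondary Aim analyses do not use it.

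**Working it through.** **Rater counts.** The plan's figures reproduce: 30 × 2 = 60 leaders, and 30 × 2 to 30 × 5 = 60 to 150 CM providers. The plan gives no power, alpha or variance figure for mediation.

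**Leader weight.** With n providers and 2 leaders, N = n + 2 and the leader share is p = 2/(2 + n). If leader self-ratings rise by d in E-ATTC and provider ratings do not move, the center mean rises by p × d.

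**Falsely mediated share.** Assumptions, none from the documents:
- true center SD 0.5 and rater SD 0.6 on the 5-point scale;
- outcome slope of 2 CM sessions per scale point within arm;
- condition effect of 2 sessions;
- no true effect of condition on engagement.

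The reliability of the center mean is R = 0.25/(0.25 + 0.36/N), so the within-arm slope on the observed score is 2R. The false share is p × d × 2R / 2 = p × d × R.

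| Providers n | p | R | Score shift, d = 0.5 | False share, d = 0.5 | False share, d = 1.0 |
|---|---|---|---|---|---|
| 2 | 0.50 | 0.735 | 0.25 | 18% | 37% |
| 3 | 0.40 | 0.776 | 0.20 | 16% | 31% |
| 4 | 0.33 | 0.806 | 0.17 | 13% | 27% |
| 5 | 0.29 | 0.829 | 0.14 | 12% | 24% |

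The average over the four sizes is about 15% for d = 0.5 and 30% for d = 1.0. A simulation with 15 centers per arm and mixed center sizes (4,000 runs per setting) gave 15% and 29%.

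**The agreement cut-off.** Take r_wg = 1 − s²/2, where 2 is the variance of a uniform response on five points (assumed; the plan names no null distribution). A center is dropped when s² exceeds 0.8. A leader-staff gap of d lowers r_wg by N p(1 − p)d² / [2(N − 1)]: 0.03-0.04 at 0.5 point and 0.12-0.17 at 1.0 point. With rater SD 0.6, the chance that a center is dropped is:
- no gap: 4-8%;
- 0.5 point: 7-14%;
- 1.0 point: 23-34%.

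Repeating the simulation with the cut-off applied again gave about 15% and 30%. The retained centers still carry the shift. Because coaching would open the gap only in E-ATTC, the exclusions would also fall more heavily on that arm.

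**The planned test.** A separate simulation used SDs of 0.5, a total effect of 0.5 SD, 3 providers per center, a 1.0-point leader shift, the cut-off applied and two-sided alpha 0.05 (all assumed). The Freedman-Schatzkin test declared positive mediation as follows:
- within-arm correlation 0.5: 61% of runs with pooled scoring, 14% with provider-only scoring;
- within-arm correlation 0: 2.2% and 0.8%.

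At a correlation of .18, without the cut-off, the pooled rates were 7% and 11% for shifts of 0.5 and 1.0 point, against 3% for provider-only scoring. The β of .18 in 9.c.ii is a staff-level coefficient, so it is only a rough guide to that value.

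**The case against.** **The measure is defined as the perceptions of both groups.** Much of the coaching in 7.b concerns funding, contracts and sustainment planning, where real change may be visible to leaders and not to providers. Treating provider ratings as the truth is a choice. This stands, and it is why the provider-only score should sit beside the all-rater score and not replace it.

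**Providers are unblinded too.** E-ATTC staff receive bonuses and know it. A 0.25-point condition-related bias in provider ratings would give a false share of about 17% under provider-only scoring: 0.25 × R, with R = 0.25/(0.25 + 0.36/n) averaging 0.69 over n = 2 to 5. A reader might infer that provider-only scoring removes the bias. It removes only the leader self-rating component; a zero false share under it follows from assuming unbiased providers.

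**The cut-off is a safeguard.** It is a partial one: it drops a quarter to a third of affected centers at a 1-point gap. A reader might infer that it does nothing, which is wrong, or that it protects the estimate, which the calculation does not support.

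**The plan does not say outright that leaders are averaged in.** Section 10.c speaks only of staff-level responses. That leaders are included is a strong inference from 8.b and 9.c, not a stated rule.

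**The magnitudes are assumed, and the test is itself liberal.** Both are true. The 14% rate under provider-only scoring arises with no change seen by staff, so not all of the 61% is due to leader ratings. Doubling the condition effect to 4 sessions halves the false share.

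**Climate.** A reader might extend the point to Implementation Climate, which 9.c.i defines as "the extent to which the innovation being implemented (i.e., CM) is expected, supported, and rewarded within their center", because only E-ATTC pays for CM. The documents do not support that extension. Section 7.b says "E-ATTC condition CM staff will have the opportunity to earn monetary bonuses for the achievement of two performance measures", so front-line staff do experience the change, and reward is part of the construct as defined. What remains is an overlap between mediator content and an intervention component.

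**Conclusion.** The concern holds for Leadership Engagement, with conditions. If leaders enter the center score, as 8.b and 9.c indicate, they supply 29-50% of it, and a leader-only shift can be reported as mediation with no change seen by staff. This also requires that the score predict the outcome within arm; without that relation the false-mediation rate stays low. The 15% and 30% shares illustrate the mechanism under assumed SDs, slope, effect and shifts. They are not forecasts for this trial.

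The documents do not show that leaders' self-ratings will be inflated, nor that a rise in them would be spurious. The point is that the planned score cannot tell the two apart. The aim is exploratory and the remedy is cheap, so this is a worthwhile improvement and not a threat to the trial's main conclusions.

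**What to change.** In 9.c.ii and 10.c:
1. State which raters enter the center Leadership Engagement score.
2. Compute the score and its r_wg from CM-provider ratings as well as from all raters.
3. Report leaders' self-ratings separately by arm.
4. Run the mediation model with both scores. Claim leadership-engagement mediation only if the provider-rated score supports it; otherwise report the result as dependent on leader self-report.

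Optionally, in 9.c.i and 10.c, show the climate mediation with and without the reward items, beside the published full-scale mean.

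**Cost.** Revised wording and one extra exploratory model per outcome (more if the climate option is taken), with no new data. The provider-only score rests on 2-5 raters instead of 4-7, so its rater-error variance is (n + 2)/n = 1.4 to 2.0 times larger. It may miss leader-level change that providers cannot see, and it does not remove bias from providers who know their condition.

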The goal of this study is to compare two comprehensive strategies to promote CM implementation as an adjunct to pharmacotherapy within OUD centers. Using a cluster randomized design, 30 OUD treatment centers across New England will be randomized to one of the two implementation conditions: 1) ATTC control condition: SAMHSA-funded Addiction Technology Transfer Centers (i.e., didactic workshop + performance feedback + staff coaching); 2) E-ATTC experimental condition: ATTC strategy enhanced by external leadership coaching (ELC; i.e., leadership coaching focused on sustainment planning) and pay-for-performance (P4P; i.e., monetary bonuses for achieving pre-defined implementation goals). Specific research aims of the study are:

1. Primary Aim: To test effectiveness of E-ATTC, relative to the ATTC condition, on implementation outcomes.

- a. Primary Hypothesis: Relative to ATTC, E-ATTC will achieve superior: CM Exposure (i.e., patient-level measure of number of CM sessions received during 9-month Implementation phase) CM Competence (i.e., staff-level measure of CM quality during 9-month Implementation phase), and CM Sustainment (i.e., patient-level measure of number of CM sessions received during 12-month Sustainment phase).

2. **Secondary Aim:** To test effectiveness of E-ATTC condition, relative to ATTC, on patient outcomes.
 - a. Secondary Hypothesis: Relative to ATTC, E-ATTC will achieve superior: Opioid Abstinence (i.e., days of abstinence) and Opioid-Related Problems (i.e., count of problems) at 3 and 6-month follow-up.
3. **Exploratory Aim:** To test the extent to which theorized mechanisms of change (i.e., implementation climate, leadership engagement) mediate the implementation condition (i.e., ATTC vs. E-ATTC) to outcome (i.e., implementation outcome, patient outcome) relationship.
 - a. Exploratory Hypothesis: Implementation climate and leadership engagement will partially mediate the relationship between implementation condition and each outcome in the Primary and Secondary Aims.

B) Detailed Study Methodology

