1. **Study Purpose.** The primary purpose of this study is to experimentally evaluate two different comprehensive training models to train opioid treatment centers in an evidence-based behavioral treatment called contingency management (CM), which is the provision of motivational incentives for reaching specific treatment benchmarks. An exploratory goal of this study is to test whether theorized mechanisms of change – implementation climate and leadership engagement – mediate the effect of implementation condition on outcomes. Conduct of this study will address critical public health needs by (a) informing how CM, an evidence-based practice, should be implemented in OUD treatment centers, (b) improving the outcomes of OUD patients receiving treatment in the community, and (c) advancing knowledge about why and how implementation strategies work.
2. **Overview of Study Design.** A Type 3 Hybrid Trial will be conducted collecting data on both implementation and patient outcomes. We will use a 3-cohort staggered cluster RCT design. The unit of randomization will be opioid treatment centers. Centers will receive one of two comprehensive training conditions: the standard training provided by the New England Addiction Technology Transfer Center (ATTC training) or an enhanced condition that also provides leadership coaching and provider incentives (E-ATTC training). The primary research activities will be measuring the effectiveness of the training initiatives by gathering data from organizations, providers and patients.

Every 12-16 months, 10 OUD centers will be randomly selected to initiate study activities (10 centers X 3 cohorts = 30 centers). Prior to randomization, each center will complete a Baseline Organizational Assessment (described further in the Measures section) to collect organizational background data (e.g., years in operation, number of patients served annually, number of staff, medications prescribed, implementation readiness). Using these data, urn randomization procedures (balancing on number of patients served and percent of patients receiving methadone) will be used to randomize centers to either the ATTC or the E-ATTC condition. Centers in both conditions will complete a 5-month Preparation phase, a 9-month Implementation phase, and a 12-month Sustainment phase (26 months total). In both conditions, providers will record their delivery of CM in the electronic medical record and will audio record one CM session per month.

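### Section 10b lets a moderator screen over an open covariate list decide the model that tests condition, and it writes only the branch in which no moderator is found

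*Combined protocol and SAP*

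**What the plan says.** The Primary Aim (Section 2A) is "To test effectiveness of E-ATTC, relative to the ATTC condition, on implementation outcomes". The Secondary Aim has the same form for patient outcomes. No aim states a subgroup or moderation hypothesis.

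Section 10b sets the order of work. Variance is partitioned by level. Then, "following a decomposed-first strategy that advocates for starting with moderation-focused hypotheses to avoid biases associated with conflated effects", the plan says "we conduct multilevel regressions testing the extent to which our covariates significantly moderate the hypothesized relationship between condition and outcome". Covariates are given as examples at three levels: four organizational, three staff and four patient variables. The rule that follows is: "If moderation is not found, covariates will be controlled for as predictors". The section adds: "Condition assignment (ATTC vs. E-ATTC) will be the primary independent measure of interest for analyses". Statistical significance and Cohen's d are to be reported.

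No sentence covers the case in which moderation is found. Section 10b gives no significance level for the screen and no centering rule.

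Three other places bear on the covariates:

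- **Overview of Study Design:** the urn randomization is described as "balancing on number of patients served and percent of patients receiving methadone". The pre-randomization assessment is said to cover "number of staff, medications prescribed, implementation readiness", among other items.
- **Section 8b:** "After randomization, CM staff and leadership staff will complete two online Qualtrics surveys: one at the start of the Preparation phase". That first survey contains a readiness measure and CM attitudes.
- **Sections 9b.i and 9d.vi:** other drug use and global health functioning are also called covariates, but Section 10b does not name them.

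**The concern.** The main-effects model is the only condition model written for these aims, and it applies only if the screen finds nothing. If the screen finds something, several analyses fit the text: keep the interaction and report an average effect, report the effect at one covariate value, report subgroup effects, or drop the interaction. In a model with a condition-by-covariate term, the coefficient on condition depends on how the covariate is coded. Naming condition as the variable of interest therefore does not identify the number to be tested.

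That choice would be made with outcome data in hand, separately for CM Exposure, CM Competence and CM Sustainment. What is at stake is whether the primary result of a 30-center trial can be traced to a rule fixed in advance.

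**Working it through.** The plan gives no alpha, power or error rate for this step, so there is no stated figure to reproduce.

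**1. Number of screening tests.** Named covariates: 4 + 3 + 4 = 11. CM Competence is a staff-level outcome, so the four patient variables may not apply, leaving 4 + 3 = 7. CM Sustainment uses patients sampled from records, and baseline interview measures may not exist for them, so 7 to 11.

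**2. Chance that the unwritten branch is reached with no true moderator.** Assume independent tests at alpha 0.05 (neither is stated). The chance is 1 − 0.95^k.

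- k = 11: 1 − 0.95^11 = 0.431
- k = 7: 1 − 0.95^7 = 0.302
- CM Sustainment: 0.302 to 0.431

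For k = 11 the figure is 10.5% at alpha 0.01 and 68.6% at alpha 0.10. Correlated tests would lower these figures, and a longer list would raise them.

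**3. How much the choice of coefficient can matter: one example.** Take sex, with 37% female expected (Section 3d), 750 patients, equal arms, outcome SD 1 and an assumed total ICC of 0 to 0.35.

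- SE of the interaction = 2 × √((1 − ICC)/(N × 0.37 × 0.63)) = 0.151 (ICC 0) to 0.122 (ICC 0.35)
- Just-significant gap between the condition effects in men and women = 1.96 × SE = 0.30 to 0.24 SD
- Men as reference: the coefficient differs from the average effect by 0.37 × gap = 0.11 to 0.09 SD
- Women as reference: 0.63 × gap = 0.19 to 0.15 SD

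With the 80% follow-up assumed in Section 8c, N = 0.80 × 750 = 600, and the three quantities become 0.33 to 0.27, 0.12 to 0.10 and 0.21 to 0.17 SD.

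**4. Type I error for condition, patient-level null simulation.** Settings: 2,000 replicates each; 30 centers (15 per arm), 3 staff and 25 patients per center; assumed staff ICC 0.05 and center ICC 0.05, 0.15 or 0.30; variances treated as known; 11 covariates screened one at a time at 0.05, with flagged interactions kept. Sex (37%) and race/ethnicity (100 − 73 = 27% minority, Section 3d) are coded 0/1, and the other nine covariates are centered.

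| Condition effect reported | ICC 0.05 | ICC 0.15 | ICC 0.30 |
|---|---|---|---|
| Fixed main-effects model | 4.6% | 4.8% | 4.3% |
| Average effect, all centered | 4.6% | 5.0% | 4.4% |
| Read at male, White Non-Latinx | 5.3% | 5.3% | 4.7% |
| Read at female, minority | 6.9% | 6.1% | 5.1% |

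Monte Carlo error is about 1.96 × √(0.05 × 0.95/2000) = ±1.0 percentage point. A moderator was flagged in 42.1%, 43.8% and 42.7% of runs, in line with step 2.

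**5. Type I error if the effect is chosen afterwards.** A separate, simpler null simulation used 10,000 runs, 30 centers split 15:15, a center-level linear model and four center covariates only.

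- One prespecified adjusted effect: 5.1%
- Average effect always reported after screening: 5.6%
- Best of the average effect, the no-interaction effect and the effects at moderator levels: 15.4%

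**The case against.** The strongest reply is that the contrast is not really in doubt. Section 2A states the hypotheses arm against arm, Section 10a requires intent-to-treat, and Section 10b puts condition first. The average effect is then the natural reading, and step 4 shows that it keeps type I error near 5%. The decomposed-first order also has a cited rationale. Much of this stands. A reader might infer that the estimand is undefined. That goes too far: what is missing is the coefficient that estimates the intended contrast once an interaction is kept.

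Two other strong readings are not supported. A reader might take 43%, or the 72% to 77% obtained over all three primary outcomes (1 − 0.95^25 to 1 − 0.95^29), as a false-positive rate. It is only the chance that the model changes form, and it rests on an assumed alpha and independence. A reader might also take 15% as the plan's error rate. That figure requires picking among effects after seeing results, which the documents do not describe, although they do not rule it out. The sex example is likewise one path: with no true interaction, sex would be flagged in about 5% of trials. Nor do the documents suggest the female-and-minority reference coding behind the 6.9%.

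The reply does not supply the missing rule. The cited strategy explains why moderation is tested first, not what is reported next. The centering in Section 10c concerns the mediator. The unscreened condition model there serves the Exploratory Aim.

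**Conclusion.** The point holds as a should-fix. Section 10b makes the form of the primary and secondary condition models depend on an outcome-based screen of an open list, and it writes one branch of two. At an assumed alpha of 0.05 with independent tests, the unwritten branch would be reached by chance about 43% of the time for a patient-level outcome and 30% for CM Competence.

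Inflated type I error is not established. It stays near 5% if the mean-centered average effect is always the one reported, and it rises mainly if the effect is selected afterwards. The simulations rest on assumed ICCs and simplified models and are illustrative. The textual findings do not depend on them: the order of testing, the open list and the missing branch.

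**What to change.** For each primary and secondary outcome, prespecify one main-effects model. Test and report the average condition effect from it, and convert that effect to Cohen's d, whatever the moderator tests show.

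- **Main covariates (short, closed list):** the two urn factors (number of patients served, percent receiving methadone); a few center variables collected before randomization; and, where collected, baseline patient age, sex, race/ethnicity and problem severity.
- **Sensitivity model:** staff-survey measures collected after randomization, such as CM attitudes.
- **Readiness:** the Overview of Study Design places it before randomization and Section 8b after. Reconcile the two, and use it in the main model only if it is confirmed as collected before randomization.
- **Moderation:** keep these models as supporting analyses, from a closed list with mean-centered covariates.

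If the team prefers to keep interactions in the main model, the minimum is to state in advance that covariates are mean-centered and that the average condition effect is the reported result.

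The cost is SAP wording. Moderation results would no longer be confirmatory, and center covariates must be few with 30 centers. No data collection changes.
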